#### **1.2 Sample size**

There is no previous study to reference, the researchers have opted for a pilot study with a sample size of 28 participants.

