## **2. Research Format**

Pilot study and one group before-after design.

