If adverse events occur or if there are signs of an allergic reaction, participants will cease product usage and receive standard treatment from the institute. Severe reactions may lead to the participant's exclusion from the study.

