**Research Outcomes:**

6.1 Primary Outcome: Measurement of five parameters, including skin moisturization, skin elasticity, skin color, skin wrinkle assessment, and facial imaging using the Visia-CR system. Measurements will be taken at baseline, 2 months, 3 months, and 4 months.

6.2 Secondary Outcomes:

1) Assessment of participant satisfaction post-treatment at 2, 3, and 4 months using a quartile grading system (0 = unsatisfied, 1 = slightly satisfied, 2 = satisfied, 3 = very satisfied).

2) Evaluation of adverse events, including irritation, rash occurrence, new dark spots, and infections post-treatment through videocall applications at 2 weeks and 4 weeks. On-site evaluations will occur at 2 months (after completion), 3 months, and 4 months.

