## 7. Statistical Analysis

7.1 Descriptive Statistics for General Participant Information: Descriptive statistics will be used for continuous quantitative data, presenting mean and standard deviation or median and interquartile range (IQR). For non-continuous quantitative data and qualitative data (ordinal scale, nominal scale), results will be reported as percentages.

7.2 Primary Outcome Analysis: The primary outcome data, comparing values for skin moisturization, water loss from the skin, skin elasticity, skin color measurement, and wrinkle assessment before and after using the serum at 8 weeks, 12 weeks, and 16 weeks, will be analyzed. If the data follow a normal distribution, a repeated-measure ANOVA will be used, with  $p < 0.05$  considered statistically significant. In cases where the data distribution is not normal, the Wilcoxon signed-rank test will be employed.

7.3 Descriptive Statistics for Adverse Events: Descriptive statistics, reported as percentages, will be used to analyze adverse events after using the serum with Epidermal Growth Factor.

7.4 Descriptive Statistics for Participant Satisfaction: Descriptive statistics, reported as percentages, will be used to analyze participant satisfaction after using the serum with Epidermal Growth Factor.

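### Severe reactors may be excluded with no rule for counting them, so the primary result covers only those who tolerated the serum and the adverse-event rate can be understated

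*Combined protocol and SAP*

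**What the plan says.** The note at the end of section 2.1 has two tiers. After an adverse event or signs of allergy, "participants will cease product usage and receive standard treatment from the institute". Separately, "Severe reactions may lead to the participant's exclusion from the study". The note does not say whether measurements continue after the product is stopped, or what happens to the data of someone who is excluded.

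Section 6.2 makes adverse events a secondary outcome, with irritation and rash among those listed. They are sought "post-treatment through videocall applications at 2 weeks and 4 weeks", and then in person: "On-site evaluations will occur at 2 months (after completion), 3 months, and 4 months". Section 7.3 gives the whole analysis: "Descriptive statistics, reported as percentages, will be used to analyze adverse events after using the serum with Epidermal Growth Factor".

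For the primary outcome, section 7.2 compares baseline with 8, 12 and 16 weeks. If the data are normal, "a repeated-measure ANOVA will be used"; otherwise the Wilcoxon signed-rank test is used. No section defines a safety set, an efficacy set, a denominator for the percentages or a rule for missing visits.

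The design in section 2 is "Pilot study and one group before-after design". In section 1.2, "the researchers have opted for a pilot study with a sample size of 28 participants"; no allowance for dropout is given.

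**The concern.** The note makes leaving the study depend on tolerability, which the study itself sets out to measure. Two consequences follow from the text.

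- **Efficacy.** A participant excluded before week 8 has no post-baseline visit and contributes nothing to section 7.2. The same happens to someone who only stops the product if follow-up lapses, since the note does not say that measurements continue. The primary result then describes people who tolerated the serum, not everyone who started it.
- **Safety.** An excluded participant can lose the on-site evaluations at 8, 12 and 16 weeks. Because section 7.3 names no denominator, that person's event may or may not appear in the reported percentage.

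There is no control group whose losses could be compared, and with 28 people one or two exclusions move a percentage visibly. If the counting rule is left open, it can be chosen after the events are known.

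**Working it through.** **Figures in the plan.** The only relevant one is N = 28 (section 1.2). It is a declared pilot choice with no calculation behind it, so there is nothing to reproduce. The documents give no expected reaction rate and no outcome difference between excluded and retained participants. The counts and gaps below are assumptions, shown over a range.

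**Adverse-event rate.** Let k be the severe reactors who are excluded and a the other participants with an event. Three counting rules are compatible with section 7.3:

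- all who applied the serum: (k + a)/28
- excluded people removed from numerator and denominator: a/(28 − k)
- events kept, denominator cut to those remaining: (k + a)/(28 − k)

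| k | a | All treated (exact 95% CI) | Removed from both | Events kept, denominator cut |
|---|---|---|---|---|
| 1 | 2 | 3/28 = 10.7% (2.3–28.2) | 2/27 = 7.4% | 3/27 = 11.1% |
| 2 | 0 | 2/28 = 7.1% (0.9–23.5) | 0/26 = 0% | 2/26 = 7.7% |
| 2 | 1 | 3/28 = 10.7% (2.3–28.2) | 1/26 = 3.8% (0.1–19.6) | 3/26 = 11.5% |
| 2 | 2 | 4/28 = 14.3% (4.0–32.7) | 2/26 = 7.7% | 4/26 = 15.4% |
| 4 | 2 | 6/28 = 21.4% (8.3–41.0) | 2/24 = 8.3% | 6/24 = 25.0% |

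Intervals are Clopper-Pearson. Removing reactors from both parts lowers the rate in every row; keeping their events but cutting the denominator raises it slightly. Counting all treated has neither distortion.

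**Who enters section 7.2.** Standard repeated-measures ANOVA needs all four visits (day 1 and weeks 8, 12 and 16), so one missing visit removes the participant. The signed-rank test needs only the two visits of the pair being compared, but exclusion before week 8 removes all three pairs.

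**Efficacy shift.** Let R be the mean change in those retained and E the mean change in those excluded. The all-participant mean is [(28 − k)R + kE]/28. The retained mean exceeds it by (k/28)(R − E). With the gap R − E in SD units, positive when those excluded would have changed less:

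- k = 2, gap −0.5: (2/28)(−0.5) = −0.036 SD
- k = 2, gap 0: no shift
- k = 2, gap +0.5: +0.036 SD
- k = 2, gap +1.0: +0.071 SD
- k = 4, gap +1.0: (4/28)(1.0) = +0.143 SD

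Size and sign both depend on a gap that the documents do not give.

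**The case against.** A reader might infer that the plan biases the adverse-event rate down and the efficacy means up. The documents do not support that as a flat statement, for these reasons:

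- Exclusion is discretionary and concerns participation. Nothing says that an excluded person's event is deleted. Section 7.3 covers events after use of the serum, and a reaction that led to exclusion is such an event.
- The video calls at weeks 2 and 4 fall during the treatment period, and a reaction has to be known before it can lead to exclusion. Early reactions may well be on record.
- One of the three counting rules raises the rate, and one leaves it unbiased. Reporting percentages does not itself cause bias; the missing counting rule leaves room for it.
- It is tempting to say that two exclusions inflate the mean change by 28/26, or 7.7%. That holds only if those two had exactly zero change. For water loss and melanin index a favourable bias would be a lower value, and the wrinkle grade starts at 1, so the ratio does not carry over.
- Severe reactions may be few: section 1.4 excludes people with component allergy or inflammatory skin disease, and section 3 requires an irritation test before the study begins.

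All of this stands, and it removes the claim of a certain direction. It does not remove the defect. The plan still ties study exit to a measured outcome, uses methods that drop those who leave, and does not say how their events are counted. That the safety analysis is descriptive and secondary limits the consequence, but the loss from section 7.2 affects the primary outcome.

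**Conclusion.** The point holds in a limited form. As written, and assuming standard handling of missing visits, the primary comparison is restricted to participants who tolerated the serum well enough to complete it. Severe reactors can lose their 8-, 12- and 16-week safety evaluations. The adverse-event rate can be understated if their events are not counted: with 3 reactors of 28 and 2 excluded, the same data support anything from 3.8% to 11.5%, against 10.7% when all treated are counted.

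The reaction counts are assumptions. That excluded participants would have shown less benefit is plausible but not established; for two exclusions and gaps from −0.5 to +1.0 SD, the shift in a mean runs from −0.036 to +0.071 SD. The safety percentage is thus the more sensitive of the two. The gap should be closed before data are collected, because the remedy is cheap and a counting rule chosen afterwards is hard to defend.

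**What to change.** Leave the clinical decisions on stopping the product and on withdrawal as they are. Add the following:

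1. **Note in section 2.1.** Participants who stop the product for a reaction are still invited, if willing, to the measurements and adverse-event checks already scheduled. This fits the design, since step 11 already measures everyone off the serum at months 3 and 4.
2. **Section 7.3.** The denominator is everyone who applied the serum at least once. Every event counts, including those that led to stopping or exclusion. Report n/N with an exact 95% CI.
3. **Section 7.2.** Replace complete-case repeated-measures ANOVA with a linear mixed model for repeated measures that uses all available visits. Report how many stopped or left because of reactions. The linear model suits the instrument readings; the wrinkle grade scores improvement, so its handling of missing visits should be stated separately.

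The mixed model uses partial data but cannot replace visits that never took place, so the first item matters as much as the third.

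The cost is a few sentences in the plan, slightly more analysis work, and possibly a less favourable adverse-event rate or mean change. No visits are added and the sample size stays at 28.

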### 3. The materials and equipment

**Tested Product:**

Objective: Serum containing 75 ppm Epidermal Growth Factor (EGF)

Composition:

0.5% Acrylate Copolymer (Thickener)

0.5% Triethanolamine (TEA) (Neutralizer)

Phenoxyethanol / Chlorphenesin (Preservative)

Deionized Water (Solvent)

EGF 75 ppm

**Safety Standards and Packaging:**

- The product must adhere to safety standards, be free from contaminants, and not contain harmful substances. The product will undergo Microbiology Test (contamination test) by ALS and Irritation Test by DermScan Asia before testing begins.
- Phototoxicity testing is not required based on research by Henry et al., indicating no phototoxicity in the proteins present in the product (25).
- Cytotoxicity testing of rh-EGF by NSTDA showed minimal contamination below injectable drug standards, and animal testing indicated no cytotoxicity.
- The product will be stored according to the sponsor company's recommendations, at a temperature below 30 degrees Celsius, avoiding sunlight, and has an approximate shelf life of 2 years.

**Equipment:**

Temperature and Humidity Control Room:

Objective: Maintain conditions at  $20\pm3^{\circ}\text{C}$  and  $50\pm3\%$  RH.

**Tewameter TM 300:**

Manufacturer: Courage & Khazaka (C&K) Electronic GmbH, Germany

Purpose: Measures transepidermal water loss (TEWL) from the skin.

**Corneometer CM 825:**

Manufacturer: Courage & Khazaka (C&K) Electronic GmbH, Germany

Purpose: Measures skin hydration.

**Cutometer MPA580:**

Manufacturer: Courage & Khazaka (C&K) Electronic GmbH, Germany

Purpose: Measures skin elasticity.

**Mexameter MX18:**

Manufacturer: Courage & Khazaka (C&K) Electronic GmbH, Germany

Purpose: Measures melanin index (MI) for skin color.

**Visioscan VC98:**

Manufacturer: Courage & Khazaka (C&K) Electronic GmbH, Germany

Purpose: Measures skin wrinkles.

**Visia-CR:**

Manufacturer: Canfield Scientific, Inc., US

Purpose: Captures detailed facial images for before-and-after comparisons.

**4. Table of activities:**

Activities	Day/wk	d1	2 wk	4 wk	8 wk	12 wk	16 wk
Record data		✓					
Apply EGF serum		✓	✓	✓	✓		
Apply sunscreen cream		✓	✓	✓	✓	✓	✓
Measuring skin moisture and water loss using Tewameter and Corneometer		✓			✓	✓	✓
Measuring skin elasticity using Cutometer		✓			✓	✓	✓
Measuring melanin index using Mexameter		✓			✓	✓	✓
Measuring wrinkle using Visioscan		✓			✓	✓	✓
Capturing facial images using Visia-CR		✓			✓	✓	✓
Evaluation by Specialists (Two Board-Certified Dermatologists)					✓	✓	✓
Assessment of Participant Satisfaction					✓	✓	✓
Assessment of adverse effects					✓	✓	✓

Assessment of adverse effects via videocall application line		✓	✓			
--	--	---	---	--	--	--

## 5. Informed Consent Process

Before volunteers participate in the research project, the researcher will explain the research objectives, methodology, potential risks or side effects of the research, treatment, anticipated benefits from the research, and inform the volunteers of their right to voluntarily choose to participate or withdraw from the research at any time without coercion. Volunteers will be assured of medical care accessibility during and after participation. Once the volunteers decide to join, they will sign a consent form, certifying their voluntary participation in the research project.

## 6. Data Collection

Data collection for all participant types will commence after obtaining approval from the ethics committee at the Institute of Dermatology, and information will be gathered through the following:

**Participant Assessment Data:**

Pre-research assessment (baseline) and post-treatment assessments at 2, 3, and 4 months.

**Research Outcomes:**

6.1 Primary Outcome: Measurement of five parameters, including skin moisturization, skin elasticity, skin color, skin wrinkle assessment, and facial imaging using the Visia-CR system. Measurements will be taken at baseline, 2 months, 3 months, and 4 months.

6.2 Secondary Outcomes:

1) Assessment of participant satisfaction post-treatment at 2, 3, and 4 months using a quartile grading system (0 = unsatisfied, 1 = slightly satisfied, 2 = satisfied, 3 = very satisfied).

2) Evaluation of adverse events, including irritation, rash occurrence, new dark spots, and infections post-treatment through videocall applications at 2 weeks and 4 weeks. On-site evaluations will occur at 2 months (after completion), 3 months, and 4 months.

## 7. Statistical Analysis

7.1 Descriptive Statistics for General Participant Information: Descriptive statistics will be used for continuous quantitative data, presenting mean and standard deviation or median and interquartile range (IQR). For non-continuous quantitative data and qualitative data (ordinal scale, nominal scale), results will be reported as percentages.

7.2 Primary Outcome Analysis: The primary outcome data, comparing values for skin moisturization, water loss from the skin, skin elasticity, skin color measurement, and wrinkle assessment before and after using the serum at 8 weeks, 12 weeks, and 16 weeks, will be analyzed. If the data follow a normal distribution, a repeated-measure ANOVA will be used, with  $p < 0.05$  considered statistically significant. In cases where the data distribution is not normal, the Wilcoxon signed-rank test will be employed.

7.3 Descriptive Statistics for Adverse Events: Descriptive statistics, reported as percentages, will be used to analyze adverse events after using the serum with Epidermal Growth Factor.

7.4 Descriptive Statistics for Participant Satisfaction: Descriptive statistics, reported as percentages, will be used to analyze participant satisfaction after using the serum with Epidermal Growth Factor.

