## 6) Evaluation Parameters

Five parameters will be measured using various tools to assess experiment results.

Measurement of skin moisture and water loss using Corneometer and Tewameter, respectively.

Measurement of skin elasticity using Cutometer.

Measurement of skin color using Mexameter.

Evaluation of skin wrinkles using Visioscan.

[figure not shown]
Assessment of facial skin changes using Visia-CR imaging.

These steps are meticulously designed to ensure high-quality and reliable data for the dermatological research.

The measurements for Corneometer, Tewameter, and Cutometer will be taken at four specific positions:

- Right Malar prominence area
- Left Malar prominence area
- Central forehead
- Central chin

Measurements will be performed three times at each position, as illustrated in the diagram below. Each volunteer will calculate the average value for all four areas to represent their data. Assessors will use a marking technique on transparent sheets to ensure consistent measurement points are maintained across all sessions.

[figure not shown]

The positions for measurements using Corneometer, Tewameter, and Cutometer

When using the Mexameter to measure the Melanin Index (MI), readings will be taken at two specific positions:

- Right Malar prominence area
- Left Malar prominence area

Measurements will be conducted three times at each position, as depicted in the diagram below. Each volunteer will calculate the average value for both areas to represent their data. Assessors will utilize a marking technique on transparent sheets to ensure consistent measurement points across all sessions.

The positions for measurements using Mexameter

Visioscan is used to assess wrinkles using a 4-grade percentage wrinkle improvement scale as follows:

Grade 1 (0-25%): No change to a slight improvement in wrinkles.

Grade 2 (> 25-50%): Moderate improvement in wrinkles.

[figure not shown]
Grade 3 (50-75%): Marked improvement in wrinkles.

Grade 4 (>75%): Significant to no wrinkles.

The assessment involves scoring at four positions:

- Right crow feet area
- Left crow feet area
- Right cheek line area
- Left cheek line area

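### Section 7.2 tests several unranked primary measures at three visits with no success rule, multiplicity adjustment or exploratory label; its before-after test does not fit the wrinkle grade, and Visia-CR has no analysis

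*Combined protocol and SAP*

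**What the plan says.** Section 6.1 makes several things primary and ranks none of them: "Primary Outcome: Measurement of five parameters, including skin moisturization, skin elasticity, skin color, skin wrinkle assessment, and facial imaging using the Visia-CR system". They are measured at baseline and at 2, 3 and 4 months.

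Section 7.2 tests "skin moisturization, water loss from the skin, skin elasticity, skin color measurement, and wrinkle assessment before and after using the serum at 8 weeks", then repeats the comparison at weeks 12 and 16. If the data are normal, the test is a repeated-measures ANOVA with p<0.05 as the criterion. Otherwise: "In cases where the data distribution is not normal, the Wilcoxon signed-rank test will be employed". No order of testing, main visit, success rule or adjustment appears in either section.

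The two lists differ. Water loss is in 7.2 but not named in 6.1, although Section 2.1, item 6 puts it on one line with moisture: "Measurement of skin moisture and water loss using Corneometer and Tewameter, respectively". Visia-CR is in 6.1 but not in 7.2. Sections 7.3 and 7.4 cover only adverse events and satisfaction.

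On wrinkles, Section 2.1, item 6 says: "Visioscan is used to assess wrinkles using a 4-grade percentage wrinkle improvement scale as follows". The table of activities (Section 4) schedules the Visioscan measurement on day 1 and at weeks 8, 12 and 16. It schedules the dermatologists' evaluation only at weeks 8, 12 and 16.

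On status, Section 1.2 says "the researchers have opted for a pilot study with a sample size of 28 participants" and Section 2 says "Pilot study and one group before-after design".

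**The concern.** A reader of the final report will want to know which result is the primary one, and the plan cannot say. The visits also mean different things: week 8 is the end of serum use, while weeks 12 and 16 follow its withdrawal (Section 2.1, items 8 to 11). With several measures, three visits and no ranking, the authors could report whichever comparison is significant as the primary finding, and 5% would not be the error rate of that claim.

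The number of tests is not fixed either. A repeated-measures ANOVA gives one overall test per measure. The signed-rank test compares two time points, so replacing the ANOVA with it can mean three baseline comparisons per measure. Which applies depends on a normality check made after the data are seen.

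Two further gaps do not depend on any error-rate calculation. A before-after test needs a before value, and an improvement grade has none. And one of the five named primary parameters, Visia-CR imaging, has no stated analysis.

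**Working it through.** The documents state no power, family-wise error or correlations, so there is no plan figure to reproduce. The results below are conditional on stated assumptions.

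**Inputs**
- Sample size 28 (Section 1.2), taken with no dropout.
- Level 0.05 (Section 7.2, stated with the ANOVA). Assumed two-sided, and assumed to apply to the Wilcoxon test too.
- Measures with a baseline value: moisture, water loss, elasticity and melanin index, so 4 (Section 2.1, item 6; Section 4).
- Visits at months 0, 2, 3 and 4, so 3 comparisons with baseline (Sections 6.1 and 7.2).
- Assumed: no true change, and any one significant test counts as success.

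**Number of tests.** ANOVA: 4 × 1 = 4. Wilcoxon, each later visit against baseline: 4 × 3 = 12.

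**Independent tests.** Four: 1 − 0.95^4 = 0.185. Twelve, if all were independent: 1 − 0.95^12 = 0.460. The twelve are not independent, because the three changes within a measure share one baseline.

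**Correlation between changes from a shared baseline**
- If all visits correlate equally at ρ, each change has variance 2σ²(1 − ρ) and any two have covariance σ²(1 − ρ). Their correlation is 0.5 whatever ρ is.
- If correlation decays at r per month, changes at months s and t correlate at (1 + r^|t−s| − r^s − r^t) / (2√[(1 − r^s)(1 − r^t)]).
  - r = 0.7, months 2 and 4: 0.7599 / (2√[0.51 × 0.7599]) = 0.61.
  - r = 0.9, months 3 and 4: 0.5149 / (2√[0.271 × 0.3439]) = 0.84.

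**Simulated chance of at least one false positive** (20,000 null trials per setting, uncorrected ANOVA, exact Wilcoxon)

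| Correlation between visits | 4 ANOVAs, measures independent | 12 Wilcoxon, measures independent | 4 ANOVAs, measures at 0.8 | 12 Wilcoxon, measures at 0.8 |
|---|---|---|---|---|
| Equal | 18.9% | 40.2% | 11.8% | 26.8% |
| Decay 0.7 per month | 22.9% | 36.4% | 14.1% | 23.5% |
| Decay 0.8 per month | 23.9% | 35.4% | 15.0% | 23.0% |
| Decay 0.9 per month | 25.2% | 34.4% | 15.5% | 22.2% |

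The Monte Carlo standard error is at most √(0.4 × 0.6 / 20,000) = 0.35 percentage points. Separate runs of the equal-correlation Wilcoxon case with independent measures gave 40.6% and 41.0%, hence 41% as the upper end. The ANOVA figures rise under decay because sphericity fails. With a Greenhouse-Geisser correction they are 17-18% (independent) and 11% (0.8).

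**Week 8 only, four Wilcoxon tests.** Unadjusted: about 18% (independent) and 11% (0.8). With Holm: about 5% and 3%.

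**Power cost of Holm.** The strictest step is 0.05/4 = 0.0125. For a paired t test with n = 28, 27 degrees of freedom, noncentrality d√28 and 80% power, d = 0.549 SD of the change at 0.05 and 0.670 SD at 0.0125. For the exact Wilcoxon test on normal data the values are about 0.57 and 0.69.

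**Wrinkle grade.** Grades 1 to 4 are bands of percentage improvement. Day 1 has a Visioscan measurement, but no score or instrument variable is defined for it. The documents therefore give no pair of values for the test in 7.2.

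**Visia-CR.** Section 2.1, item 6 fixes a five-point improvement scale and two raters. The nearest analysis rule is "For non-continuous quantitative data and qualitative data (ordinal scale, nominal scale), results will be reported as percentages", but it stands in 7.1, which is headed as general participant information.

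**The case against.** The strongest reply is that this is a single-arm pilot with no earlier study to draw on. Family-wise control is not obligatory in such a study, and an exploratory label would largely answer the multiplicity point. That stands, and it limits the weight of the point. It does not remove it, because 7.2 declares significance on outcomes called primary and contains no such label. Nor does pilot status supply a Visia-CR analysis or a baseline wrinkle score.

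Second, a reader might infer that the plan has a false-positive rate of 19-41%. The documents do not support that. They give no rule that one significant test is enough. If every primary measure had to succeed, the error would not be inflated at all. The percentages describe one permitted reading.

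Third, the upper Wilcoxon figures need all four measures to fail normality, three baseline tests each, and equal correlation between visits. Under decaying correlation, which is plausible for repeated visits, they fall to 34-36% and 22-24%. That is why ranges are given.

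Fourth, a reader might infer that no baseline wrinkle data are collected, or that Visia-CR is not scored. Neither is so: Visioscan is scheduled on day 1, and the Visia-CR scale and raters are set. What is missing is a before value on the wrinkle score that is defined, and an analysis of the Visia-CR scores.

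Finally, the water-loss mismatch is small. Pairing it with moisture accounts for the count of five, so only the wording needs aligning.

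**Conclusion.** The point holds as a pre-specification gap that should be closed; it does not show that the plan's error rate is wrong. Section 7.2 does not say which measure or visit carries the primary claim, and it does not call the tests exploratory.

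If one significant result were reported as the primary finding, the false-positive chance for the four instrument measures would be about 19-25% with uncorrected ANOVAs and 34-41% with Wilcoxon tests when the measures are independent. At an assumed between-measure correlation of 0.8 it would be about 12-16% and 22-27%. The ranges reflect the unknown correlation between visits. All assume n = 28 complete, two-sided 0.05 and no true change. Every setting examined exceeds 5%.

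Two findings need none of these assumptions: the before-after test cannot be applied to the wrinkle grade as defined, and Visia-CR is primary without an analysis.

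**What to change.** Before data are seen, use one matching primary list in 6.1 and 7.2, then choose one of two options:

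- (a) Name one instrument measure, as change from baseline to week 8, as the single primary outcome.
- (b) Keep moisture, water loss, elasticity and melanin index as multiple primary measures, and apply Holm at overall two-sided 0.05 to one paired week-8 versus baseline test for each. The term co-primary is best avoided, since it can mean that all must succeed.

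Under either option, fix the paired test in advance, for example the signed-rank test already named in 7.2, so that the choice does not follow a normality check.

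Make weeks 12 and 16, the wrinkle grade and the Visia-CR improvement score secondary. Summarise the two improvement scores by visit without a baseline test, and state how facial positions (for the wrinkle grade) and the two raters (for both) are combined. Averaging can give values between grades, so a plain percentage per grade is not enough by itself. Label all unadjusted results exploratory.

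Cost: no new data, but more than a change of wording. Wrinkles and Visia-CR, two of the five named primary parameters, lose primary status, and under (a) so do the other instrument measures. Under (b) the detectable paired change at Holm's strictest step rises from 0.55 to 0.67 SD (80% power, paired t).
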